attachment is confirmed, the cells will be then incubated in a non-CO2 incubator for 20 min at 37°C. The cellular bioenergetics of PBMCs or platelets will be determined by using a standard mitochondrial stress test as we previously published via consecutively injecting oligomycin, an uncoupler (FCCP), and the mitochondrial electron transport chain blockers antimycin A and rotenone into the wells as we previously published (30–37). Clinical repercussions of MD in NF1 will be measured through serial scores of fatigue and pain on the same days that PBMC and platelets are collected. Fatigue will be assessed through the Functional Assessment of Chronic Illness Therapy-Fatigue (FACIT-F). FACIT-F is the only fatigue scale that has been validated in dermatological and painful disease, as it is commonly used in neurological disorders (38). Pain will be assessed by the NRS-11 scale, as recommended by the patient-reported outcome group of the Response Evaluation in Neurofibromatosis and Schwannomatosis (REIS) (39). Other biochemical and metabolic functions to be followed will be CK, cardiac function through echocardiogram, body mass index, liver, and kidney function.

**Aim 2: Assess whether therapeutic interventions impact mitochondrial function and metabolic plasticity of circulating cells of NF1 patients.** We hypothesize that NF1 patients' inherent mitochondrial dysfunction makes them more responsive to therapeutic interventions resulting in further mitochondrial injury (e.g., by MEK inhibitors, including KOS) or improved function (e.g., by vitamin D). Most patients are vitamin D deficient so the standard of care involves supplementation that could improve mitochondrial function given its essential role in many related processes. Also, we will carry out an exploratory study on the potential adverse effects of KOS on adult NF1 patients who are beginning therapy during the study window. While promising in treatment, the use of this drug has a high incidence of significant adverse side effects like cardiotoxicity (30%). The cause for toxicity is unknown yet may involve further compromised mitochondrial function as reported for other similar tyrosine kinase inhibitors (40). The combination of these studies will provide a critical preliminary assessment of the sensitivity of the mitochondrial measures to patient interventions as well as the possible capacity to correlate with favorable or harmful outcomes.

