Subjects who present to the clinic and match the inclusion/exclusion criteria for either the NF1 or control group will be provided a copy of the consent for review. A thorough discussion of the consent will be provided by study staff. If the subject agrees to participate, the following will be completed at each of the 3 total visits required by the study. Each visit will occur at 14 weeks (+/- 2 weeks):

### Visit 1

- The subject's medical history will be gathered. This will include information regarding a subject's height, weight, medications used, vitamin D levels, kidney, liver, and heart function.
  - For control subjects, the PI will confirm that the subjects do not have NF1 by family history and physical exam.
- Questionnaires regarding pain and fatigue will be provided for the subject to review and answer.
- Standard-of-care lab draws will continue to occur.
- An additional 10 mL of blood will then be drawn for mitochondrial testing purposes.

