## **Study Population**

This study will look to enroll 40 to 45 adults over 18 years old diagnosed with NF1 as well as 10 to 15 adults over 18 years old without NF1 (the control group).

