### **Data Analysis**

XF Pro mito-stress test data will provide direct measurements of basal, nonmitochondrial, and maximum respiration, and we will use these data to calculate the mitochondrial basal respiration, ATP-linked respiration, reserve respiratory capacity, proton leakage, and coupling efficiency in PBMCs and platelets isolated from the control group once and from NF1 patients longitudinally (3 times). At the end of each run, we will also determine the cellular bioenergetics and metabolic plasticity (switch between oxidative phosphorylation and glycolysis) of the cells via plotting extracellular acidification rate versus oxygen consumption rate. The NF1 and healthy control groups' mitochondrial function and metabolic plasticity parameters will be compared in addition to longitudinal changes in these parameters for each NF1 patient. Linear regression analysis will be utilized to establish the relationship between coupling efficiency, respiratory capacity (ATP-linked, reserve capacity etc.) as well as metabolic plasticity and NF1 clinical phenotype and biochemical scores for fatigue, pain, CK, cardiac function, BMI, and liver function. Analysis of variance for repeated measures will also be used to analyze changes in these parameters over time by each group (NF1 patients before and after Vitamin D and/or KOS administration).

This pilot study was designed to test the feasibility of our recruitment and implementation procedures and operational strategies. Preliminary data obtained from this pilot project will also be used to assess the variability of outcomes for power analysis of future larger studies. A biostatistician will be consulted during pilot data analysis and included in the team for statistical power calculations for future studies.

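### Repeated-measures ANOVA suits the before-after treatment comparison poorly; a mixed model using every draw, with time-varying exposure, would be a cheap improvement

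*Combined protocol and SAP*

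**What the plan says.** The Data Analysis section names one method for change over time within NF1 patients: "Analysis of variance for repeated measures will also be used to analyze changes in these parameters over time by each group". It describes the groups as "NF1 patients before and after Vitamin D and/or KOS administration". Samples are "isolated from the control group once and from NF1 patients longitudinally (3 times".

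The Study Design and Procedures section sets three visits and gives the spacing as "Each visit will occur at 14 weeks (+/- 2 weeks". Under Aim 2, the KOS work concerns "adult NF1 patients who are beginning therapy during the study window". The Study Population section gives the NF1 target: "This study will look to enroll 40 to 45 adults over 18 years old diagnosed with NF1". The sizes of the vitamin D and KOS subgroups are not stated.

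The documents have no rule for missed visits, dropout or unusable samples, and name neither imputation nor a mixed model. Medications are listed for collection at Visit 1. The lists for Visits 2 and 3 contain only questionnaires, routine laboratory draws and the research blood sample.

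**The concern.** Two features of the design sit badly with conventional repeated-measures ANOVA.

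The first is incomplete data. Draws take place at routine appointments over three visits, so some missed draws are likely. The conventional analysis needs a full row per patient, so one missing draw removes that patient's other draws too.

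The second is staggered treatment. Patients may start KOS or vitamin D between Visits 1 and 2 or between Visits 2 and 3, and may have neither, one or both at a given draw. With visit as the factor, Visit 2 is an after-treatment draw for some patients and a before-treatment draw for others. A missing-data rule alone would not cure that.

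At stake are the precision and clarity of the Aim 2 before-after estimates. The variability estimates that the pilot is meant to pass on are also affected: "Preliminary data obtained from this pilot project will also be used to assess the variability of outcomes for power analysis of future larger studies".

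**Working it through.** The plan gives no significance level, power, standard deviation, dropout rate or derivation of its sample size, so it has no figure to reproduce. What follows is illustrative.

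**Inputs from the documents.** Three draws per NF1 patient; 40 to 45 NF1 patients.

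**Assumptions.** Visit 1 is always observed, since consent and the first sample fall on the same day. Visits 2 and 3 are each missed independently with probability m. Any two draws correlate at rho = 0.5 with equal variances. The test is two-sided at 0.05 with 80% power, using a normal approximation.

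**Step 1: complete patients, three-visit form.** The expected number is N × (1 − m)².

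| m | Proportion complete | Of 40 | Of 45 |
|---|---|---|---|
| 5% | 0.95² = 0.9025 | 36.1 | 40.6 |
| 10% | 0.90² = 0.81 | 32.4 | 36.5 |
| 15% | 0.85² = 0.7225 | 28.9 | 32.5 |

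At m = 10% and N = 40, the expected number of observed draws is 40 × (1 + 2 × 0.9) = 112. Those discarded with incomplete patients number 40 × (0.18 × 2 + 0.01 × 1) = 14.8.

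**Step 2: precision of the Visit 1 to Visit 3 change.** The detectable change in SD units is (1.960 + 0.842) × √variance, where the multiplier is 2.802.

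- Full data: variance 2(1 − 0.5)/40 = 0.0250, detectable change 0.44 SD.
- Complete cases, m = 10%: variance 1/32.4 = 0.0309, detectable change 0.49 SD.
- Mixed model, m = 10%: information is summed over four visit patterns (all three visits 0.81; Visits 1 and 2 only 0.09; Visits 1 and 3 only 0.09; Visit 1 only 0.01). The variance is about 0.0268 and the detectable change 0.46 SD.

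The mixed-model variance is about 13% lower (0.0268/0.0309 = 0.87), a ratio that holds for rho from 0.3 to 0.7. At m = 20% the detectable changes are 0.55 SD (complete cases) and 0.48 SD (mixed model). For a subgroup of 10 (size assumed) at m = 10% they are 0.98 and 0.92 SD; the normal approximation is optimistic at that size.

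**Step 3: mechanism.** A simulated set of 40 patients with follow-up visits missed at 10% was put through a standard repeated-measures ANOVA routine, which rejected it as unbalanced. Restriction to complete patients kept 27 of 40 patients and 81 of 107 draws; a mixed model used all 107. This shows the mechanism, not the size: about 32 complete patients were expected, so 27 was an unlucky draw.

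**Step 4: the two-level before/after form.** A patient then needs one draw on each side of the treatment start.

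- Start between Visits 1 and 2: lost only if both later visits are missed, m² = 1% at m = 10%.
- Start between Visits 2 and 3: lost if Visit 3 is missed, m = 10%.
- Three-visit form, for comparison: 1 − 0.81 = 19% lost.

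The two-level form therefore loses fewer patients, and with two levels sphericity is not an issue. But each completed patient has two draws on one side of the start, so one is dropped or the two are averaged.

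**Step 5: staggered starts in the three-visit form.** If half of the patients start before Visit 2 and half after it (assumed), a constant effect d contributes 0.5 × d + 0.5 × 0 = 0.5d to the Visit 2 mean. The visit profile then reflects the mix of start times as well as the effect.

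**The case against.** The strongest reply is that the text does not commit the sponsor to the three-visit form. It names a family of methods and describes the comparison as before versus after administration, which can be read as a two-level factor. On that reading most of the patient loss goes, sphericity is not in question, and starts are aligned by construction. A mixed model reported under the name of repeated-measures ANOVA would also avoid deletion. This stands. A reader might infer that only patients with all three visits will be analysed, but the documents do not say so; it follows only from the conventional method with visit as the factor.

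A reader might also infer that the KOS comparison will be biased because patients who feel worse miss visits. Nothing in the documents says who will miss visits or why. Draws coincide with routine care, which may help attendance. If missingness did depend on unobserved worsening, a mixed model would be biased as well.

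It is also fair that the regressions and the comparison with controls can still use a patient's available draws, that the KOS work is labelled exploratory, and that a biostatistician will be consulted at analysis. The ±2-week window does no harm to an analysis that treats visit as a category.

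What remains is that the plan does not say which form it means, neither ANOVA form makes good use of all draws under staggered starts, and a better method costs little.

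**Conclusion.** The point holds as a worthwhile, inexpensive improvement. In the conventional three-visit form, the named method drops patients with a missing draw and cannot represent starts between different visits. In the two-level form it loses fewer patients but wastes or averages a draw.

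The precision lost is modest: about 0.49 against 0.46 SD at 10% missed. That rests on an assumed miss rate, independent misses, an assumed correlation of 0.5 and N = 40. The counts in Step 1 apply to the whole NF1 group. A reader might take them as the loss in the before-after comparison, but that comparison uses treated subgroups whose sizes are not given, so the loss there cannot be stated.

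Nor do the documents support reading this as a failed power claim. The study is a pilot, states no power, and defers power calculations to later studies.

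**What to change.** In Data Analysis, replace repeated-measures ANOVA with a linear mixed model fitted by REML to all available draws. Include a random intercept per patient, actual time since Visit 1, and time-varying indicators for vitamin D and KOS exposure at each draw. Use Kenward-Roger or similar small-sample degrees of freedom, report estimates with 95% confidence intervals, and report missed draws by treatment subgroup. State that a random intercept alone assumes equal correlation between any two draws.

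In the Visit 2 and Visit 3 lists, add the recording of vitamin D and KOS start dates, as well as at Visit 1. Exposure at each draw cannot be derived reliably from a medication history taken only once.

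The cost is a few sentences and slightly more data entry, with no extra patients, visits or blood. Three limits should be stated:

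- The model is valid only if missingness depends on observed data.
- If few patients start KOS, or most start between the same two visits, time and exposure effects will be separated imprecisely.
- The number of draws needs settling first. The Aim 1 text describes sampling at consent and then every three to four months for a year, while the visit schedule and Data Analysis give three draws. These statements should be reconciled.

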## **Ethical Considerations**

This study will be conducted in accordance with all applicable government regulations and University of Arkansas for Medical Sciences research policies and procedures. This protocol and any amendments will be submitted and approved by the IRB as required.

No compensation will be given for patients or controls.

The informed consent of each subject, using IRB-approved consent materials, will be obtained before that subject begins any study procedures. All subjects for this study will be provided a paper consent form describing this study in language understandable to the study population. Consent materials will provide sufficient information for subjects to make an informed decision about their participation in this study. The person obtaining consent will thoroughly explain what the subjects need to know about the study, including study requirements, study risks and benefits. The consent process will take place during their clinic visit in the exam room. The consent discussion will occur at the same day of the first blood sample. Participant privacy will be maintained and questions regarding participation will be answered. No coercion or undue influence will be used in the consent process. This consent form must be signed by the subject, and the person obtaining the consent. The participant will receive a paper copy of the signed consent form, and the informed consent process will be documented in the research record.

The consent process will be documented separately via a written note in the research or medical chart for each subject.

## **Dissemination of Data**

Results of this project will be presented in Neurofibromatosis and Neuro-oncology symposium and Conferences, as published in neuro-oncology and metabolism journals.

